- 2) During the factorial experiment, participants will watch a video of the clinical vignette. Participants will be randomized to receive one of various versions of the vignette that have different combinations of uncertainty communication and randomized to either receive or not receive the narrative information sheet. The experiment will be delivered through University of Utah Research Electronic Data Capture (REDCap). Each participant will receive one version of the vignette. After reading the vignette and the narrative information sheet (if they are randomized to receive it), participants will be asked to answer survey questions including outcome measures, sociodemographic information about them and their child, and information about their child's past medical history (see below primary and secondary outcomes). No identifying information on the participant or their child will be collected. If participants

enroll in the study and start study procedures in-person but do not complete the study, the study team will make follow-up phone calls with the participants to help them complete the study remotely.

Randomization: 2) For the factorial experiment, we will randomize each participant to receive one of eight possible versions of the clinical vignette or clinical vignette and narrative information sheet. We anticipate possibly having up to eight versions of the vignette and/or vignette + narrative information sheet combination. Thus, $n=63$ parents will be randomized to each version. Randomization will occur through the REDCap randomization function after enrollment in the study. The participant and study team members including the PI will be blinded to which condition the participant was assigned to. While study personnel may be present during the experiment for participants who undergo in person recruitment, they will be there for technical support, the participant will complete the experiment on their own.

Study Procedures at secondary site Children's Hospital of Los Angeles:

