Children's Hospital of Los Angeles (CHLA) will be participating in study procedures. The CHLA study team has received their own independent IRB approval for all study procedures at their own institution (study number: CHLA-22-00281). For Part 1 of the study, the CHLA team will pass along the contact information of all consented CHLA participants via University of Utah REDCap to the University of Utah team for our team to complete virtual study interviews. For Part 2 of the study, the CHLA team will conduct all study procedures with CHLA participants and pass along the contact information of consented participants for the sole purpose of gift card remuneration. All data collected by CHLA will be done through UofU REDCap. The CHLA research assistant will be given limited data access to the University of Utah REDCap project: they will not be able to view University of Utah participant data and will only have access to a limited number of instruments within REDCap that are specific to the study procedures performed at CHLA. No PHI or data from the University of Utah or Primary Children's Hospital will be disclosed to CHLA. More information can be found in the CHLA IRB approved protocol document that is attached in the "Other" section of this application.

Primary outcome: Decision preparedness as measured by the PrepDM validated survey measure. The 10-item (1 to 5 scale) survey measure results in a composite mean score of all items with higher scores indicated greater patient preparedness to make a decision with their provider.

Secondary outcomes: We will collect measures of participant cognitive, affective, and behavioral responses. Cognitive outcomes include: 1) perceptions of risk (adapted from NCI HINTS), 2) perceptions of uncertainty (adapted from the NCI HINTS), 3) knowledge (newly developed). Affective (aka emotional) outcomes include: 1) worry about NMS-related risk (adapted from NCI HINTS), 2) trust in information (adapted from NCI HINTS), 3) hope (Herth Hope Index), and 4) decisional conflict (Decisional Conflict Scale). Behavioral outcomes include: 1) intention for NMS treatment (newly developed) and 2) intention for not delaying treatment (newly developed).

*Newly developed study measures and materials (vignettes and surveys) have been added in an amendment to the IRB protocol.

*Narrative information sheets used in the factorial experiment have been added in an amendment to the IRB protocol.

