Statistical Methods, Data Analysis and Interpretation

Data analysis: We will use 3 factors with two options each and a narrative information sheet for the factorial experiment. We will have 16 different study conditions. Standard psychometric analyses (e.g., Cronbach's alpha) will be used to confirm the internal consistency reliability of self-report measures. For our primary outcome variable PrepDM, we will use a 4-way ANOVA model to describe differences in decision preparedness across each factor (e.g. ambiguity, complexity, normalizing and explanatory language, and narrative information sheet) (4). We will use post-fit marginal estimation to express effect sizes (adjusted means and adjusted mean differences), which incorporates mean centering to make the main effects interpretable in the presence of factor interactions. Regression models, with main effect and interaction terms, can be fitted that are identical to a 4-way ANOVA model. We will use these to model the secondary outcomes, using binary logistic, ordinal logistic, and linear regression, depending on the level of measurement of the outcome variable, and will add race and education level as covariates in all models. We will perform exploratory analyses for populations with and without NMS and by ethnicity and language.

Sample size: In a validation study of PrepDM in orthopedic decision making, the scale had mean SD of 3.7+/-1.0 after the decision aid intervention (4). We will randomize n=46 subjects into each of the 2x2x2x2=16 cells of the 3-way factorial design (each factor at 2 levels), for a total N=736 subjects. This is a sufficient sample size to include 4 main effects, 3 two-way interactions, 2 3-way interaction, and 1 4-way interaction, without overfitting the data. This provides 95% power, using a two-sided alpha 0.05 comparison, to detect an adjusted mean difference of 3.7+/-1.0 vs. 3.4+/-1.0 (0.3 standardized mean difference) between the two levels of the factor. That is smaller than a 0.5-point difference on the scale of each item and has been achieved in previous studies of decision aids in orthopedics.

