STATISTICAL ANALYSIS PLAN

Understanding Factors in Decision Making for Children With Medical Complexity

NCT number: NCT05913206

Last reviewed: August 29, 2025

PI: [name], MS

General Considerations

This randomized factorial experiment examines the effectiveness of uncertainty communication statements and parent narratives for parents of children with medical complexity (CMC). The experiment was nested within a video vignette of a family's visit to a pediatric orthopaedic surgeon regarding potential surgery treatment of their child's neuromuscular scoliosis (NMS). The trial includes 16 possible scenarios based on 4 factors (ambiguity, complexity, normalizing and explanatory language, and narratives) with 2 levels each (present, absent). Participants underwent stratified randomization by language, site, ethnicity, and race.

Study Objectives and Hypotheses

The main objective of the study is to evaluate the effect of various uncertainty communication statements and narratives on decision readiness and additional cognitive, behavioral, and affective outcomes related to decision quality and risk perception.

We hypothesize that participants who receive uncertainty statements and/or narratives will report higher decision readiness without experiencing detrimental effects of increased worry or decreased hope. We hypothesized that these effects would be summative across factors.

Study Design

All participants were recruited from two sites. Eligible parents were at least 18 years old and had a child 0-21 years of age with medical complexity. Randomization was conducted using REDCap, a HIPAA compliant remote data capture system. Participants were not explicitly informed of their group assignment.

The specific trial arms are:

Control condition: Participants in the control condition received a vignette reflective of a typical orthopaedic surgery clinic visit to discuss neuromuscular scoliosis treatment without the addition of any uncertainty communication statements or exposure to parent narratives.

Ambiguity only: This intervention group received a vignette with ambiguity statements embedded in the video.

Complexity only: This intervention group received a vignette with complexity statements embedded in the video.

Normalizing and explanatory language only: This intervention group received a vignette with normalizing and explanatory language about uncertainty embedded in the video.

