Intention for not delaying treatment	For those participants who selected surgery as a treatment preference, the urgency with which they would like to pursue surgery.	X
Cognitive		
Risk perception	2 unique survey items scored individually on a 5-point Likert scale (1-very low to 5-very high). Based on NCI HINTS. ⁴	
Parents' Characteristics and Survey Feedback		
Demographics	Participants indicate their age, gender, race, ethnicity, language preference, relation to patient, rurality, employment status, marital status, education level, and household income. Participants also indicate their child's age, gender, race, and ethnicity.	X
Child medical history	Participants indicate their child's use of subspecialists, technology dependence, neurologic impairment, history of prematurity, history of neuromuscular scoliosis, and history of surgery for neuromuscular scoliosis.	X
Readability assessment of video	3-item Likert-scale assessment of video readability.	X
Intolerance of Uncertainty ⁵	Using the IUS-12 validated survey measure to calculate a summary composite variable and associated subdomains of prospective anxiety and inhibitory anxiety. Additional two unique Likert-based items each scored individually, based on NCI HINTS. ⁴	X
Health Literacy ⁶	Chew Health Literacy Scale: 3-item measure on a Likert scale (0-never to 4-always) with summary composite outcome score. Higher score indicates lower health literacy.	X

Numeracy ⁷	Subjective numeracy scale: 8-item measure on a Likert-based scale with a mean composite outcome. Q7 is reverse-coded.	X
Risk taking behavior scale ⁸	DOSPERT: 8-item Likert-based scale from 1-very unlikely to 5-very likely. Mean composite outcome.	X
Hope ⁹	Herth Hope Index: 12-items on a Likert scale (1-strongly disagree to 4-strongly agree). Summary composite outcome with reverse scaling for items hhi3, hhi6.	X
Preferences and values	6-item ranking question where participants are asked to rank particular values in order of most important to least important	X

Planned Data Analysis as of May 2023

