Participants who complete the study will be analyzed in the group to which they were randomized, regardless of fidelity. A two-tailed alpha level of 0.05 will be applied to all statistical tests. For the outcomes, we will use standard psychometric analyses (e.g., Cronbach's alpha) will be used to confirm the internal consistency reliability of self-report measures. For the primary outcome variable PrepDM, we will use a 4-way ANOVA model to describe differences in decision preparedness across each factor (ambiguity, complexity, normalizing and explanatory language, and narratives). We will use post-fit marginal estimation to express effect sizes (adjusted means and adjusted mean differences), which incorporates mean centering to make the main effects interpretable in the presence of factor interactions. Regression models, with main effect and interaction terms, can be fitted that are identical to a 4-way ANOVA model. We will use these to model the secondary outcomes, using binary logistic, ordinal logistic, logistic regression for proportions, and linear regression, depending on the level of measurement of the outcome variable, and add covariates including race and education level to all models. We will select covariates using the 10% rule. If we have sufficient power, we will perform exploratory analyses for populations with and without NMS and by ethnicity and language.

Although multiple outcomes will be considered, we have designated a single primary outcome. We do not plan formal multiple comparison adjustments for secondary and exploratory outcomes. Results for secondary and exploratory outcomes will be interpreted based on the overall pattern of results with the awareness that some nominally significant relationships may be false positive findings in the context of multiple analyses.¹⁰

We also do not plan formal multiple comparison adjustments for the randomized comparison between intervention groups, as these comparisons address distinct hypotheses and are thus appropriate for evaluation on a comparison wise basis.¹⁰

Missing data

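### The SAP's undefined 10% rule for choosing covariates does not suit a randomised factorial, and its open candidate list could let in measures that the exposure changes

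*SAP*

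**What the plan says.** The SAP (Planned Data Analysis as of May 2023) first specifies a 4-way ANOVA for PrepDM and names no covariates in that sentence. It then turns to regression models for the secondary outcomes, where the analysts will "add covariates including race and education level to all models". The next sentence is "We will select covariates using the 10% rule". The SAP does not say what the 10% refers to, which variables are candidates, or when they must have been measured.

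The protocol (Data analysis) has no selection rule. It "will add race and education level as covariates in all models".

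On timing, the protocol (Study Procedures, factorial experiment) says that after the vignette, and the narrative sheet if assigned, "participants will be asked to answer survey questions including outcome measures, sociodemographic information about them and their child". SAP Table 1 has a single time point. A few variables must have been known earlier, because the SAP (General Considerations) states: "Participants underwent stratified randomization by language, site, ethnicity, and race".

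Hope is treated in two ways. The protocol lists it among the affective secondary outcomes, "3) hope (Herth Hope Index)", and the SAP hypothesis is that readiness will rise "without experiencing detrimental effects of increased worry or decreased hope". SAP Table 1 nevertheless places the Herth Hope Index in the block for parent characteristics and survey feedback. That block also holds fixed demographics, child history, video readability, intolerance of uncertainty with two added items, and preferences and values.

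**The concern.** A change-in-estimate rule is a tool for finding confounders in observational data. Here all four factors are randomised. For a trait that exposure cannot alter, the expected shift in a linear-model factor effect is zero, so the rule can respond only to the following:

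- **Chance imbalance.** Covariates enter or leave according to the draw, not according to how well they predict the outcome.
- **Non-collapsibility.** In the binary and ordinal logistic models, a coefficient moves when a prognostic covariate is added, even with perfect balance.
- **Mediation.** If a factor changes a measure and the measure predicts the outcome, adjusting for it removes the mediated part of the effect. The rule tends to pick such a measure once that part exceeds 10% of the effect.

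The third is the serious one, because the candidate list is open and most of the survey follows exposure. The rule is also not operational here: with four main effects and their interactions, the SAP does not say which coefficient has to move by 10%. The adjustment set could therefore differ between outcomes and would be chosen from the outcome data.

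**Working it through.** **The plan's own figure.** The SAP attaches no figure to the rule. Its one design figure is 80% power for a 0.3 SD main effect with N = 728. With 364 at each level, SE = 2/√728 = 0.0741 and power = Φ(0.30/0.0741 − 1.96) = Φ(2.09) = 98.2%, so the stated 80% is not reproduced. The stated 91 in each of 16 cells also makes 1,456, not 728. Those are separate matters. Below, only the total of 728 (or the protocol's 736) and the 0.30 SD effect are taken from the documents. All covariate and mediator strengths are assumptions.

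**1. Mediator.** Let the factor shift the measure by a SD and let the measure predict the outcome with slope b. In a linear model, adjusting moves the factor effect from 0.30 to 0.30 − ab. The rule is met on average when ab > 0.1 × 0.30 = 0.03. Simulation with N = 728, true total effect 0.30 and the rule judged on that factor's coefficient gives:

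| a | b | ab | share of 0.30 | selected | mean estimate under the rule |
|---|---|---|---|---|---|
| 0.05 | 0.2 | 0.01 | 3% | 10% | 0.30 |
| 0.1 | 0.2 | 0.02 | 7% | 26% | 0.29 |
| 0.1 | 0.3 | 0.03 | 10% | 51% | 0.28 |
| 0.2 | 0.4 | 0.08 | 27% | 96% | 0.22 |

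If the true total effect is zero, the same mechanism produces false rejections. At N = 736 the rejection rate is 7% for a = 0.1, b = 0.3, and 13% for a = 0.2, b = 0.3, against a nominal 5%.

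**2. Fixed traits only.** For a covariate with correlation r with the outcome, chance imbalance moves the estimate with SD r × 2/√N. With r = 0.3 and N = 736 this is 0.3 × 0.0737 = 0.0221. The chance of exceeding 0.03 is P(|Z| > 1.36), about 17%; simulation gives 19%. When the true effect is zero, 10% of a near-zero estimate is easily exceeded and selection rises to about 80%. The mean estimate stays at 0.30 and type I error is 4.4% to 4.9%.

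**3. Power against a pre-specified set.** Assume eight independent covariates with r = 0.2 each, N = 728 and a true effect of 0.2 SD. Together they explain 8 × 0.04 = 0.32 of the variance.
- Unadjusted: Φ(0.2/0.0741 − 1.96) = 77%.
- All eight fixed in advance: SE = 0.0741 × √0.68 = 0.0611, and Φ(0.2/0.0611 − 1.96) = 90.5%.
- Simulated: unadjusted 77.6%, 10% rule 84.9%, all eight 89.9%. Type I error is 5.1%, 3.8% and 5.0% in the same order.

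**4. Logistic models.** Take a conditional log-odds ratio of 0.5 and a perfectly balanced baseline covariate. By numerical integration, adding the covariate raises the coefficient by 6%, 21% and 41% when its log-odds ratio per SD is 0.5, 1.0 and 1.5. A strong prognostic covariate can therefore pass the 10% mark with nothing to correct.

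**5. Which coefficient.** In the simulations at N = 736, a harmless covariate with r = 0.3 moved at least one of the four main effects by more than 10% in about 99% of runs. The other three effects were set to zero, which makes this easy. The answer thus depends heavily on a choice that the SAP does not make.

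**The case against.** The strongest defence is that the documents name only race and education as covariates, and a video can change neither. Race was a randomisation stratum and so was known before exposure. Being asked after the vignette does not turn education, income or child history into a mediator. Hope is an outcome in the protocol and part of the SAP hypothesis, which makes its use as a covariate less likely. The Table 1 block also covers survey feedback, which is a natural home for video readability without implying that it is a covariate. All of this stands.

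A reader might infer more than the text supports in four ways:

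- **That the plan will adjust for mediators.** No passage names hope, readability or any other changeable measure as a candidate. The documents only fail to exclude them.
- **That the primary result is affected.** The PrepDM sentence names no covariates. The covariate clause belongs to the secondary-outcome models, although it ends by referring to all models. The text is unclear on this.
- **That the four factors would be adjusted differently from one another.** For any one outcome they share a model and so an adjustment set. Only comparison across outcomes is affected.
- **That fixing and selecting race and education is a plain contradiction.** The SAP can be read as two fixed covariates plus selected extras. The wording needs to be settled.

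It is also fair to say that with fixed traits the rule does little harm. Type I error is slightly below nominal, and power is better than with no adjustment. At 0.30 SD with the same eight covariates, power is about 99% under the rule, against 98% unadjusted and nearly 100% with all eight. What the defence does not supply is a reason to use the rule, a definition of it, or a limit on the candidates.

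**Conclusion.** The point holds as a flaw of method with a possible, not an established, bias. It rests on reading the 10% rule as change-in-estimate. On that reading the rule has no confounding to correct, is not defined for four factors with interactions, and can be triggered in logistic models without any imbalance.

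The size depends on what enters. If only fixed traits are eligible, there is no material bias, and the cost is about 5 percentage points of power at 0.2 SD under the assumed covariates. If a measure changed by exposure is eligible, the reported effect for a true 0.30 SD lies between 0.30 and 0.22 over the strengths tabulated. The documents give no figures to place the trial within that range. Confidence is high that the rule is unsuitable and low about any particular amount of bias.

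**What to change.** In the SAP's Planned Data Analysis:

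1. Delete the 10% rule.
2. Use one fixed set in every adjusted model: the stratification variables (language, site, ethnicity and race) plus education. Of the stratification variables, only race is named as a covariate at present.
3. State that no measure exposure can change enters a model for a factor effect. Examples are hope, intolerance of uncertainty and its two added items, preferences and values, and video readability.
4. State whether the primary PrepDM model is adjusted, and align the protocol's covariate sentence with the SAP.

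This takes a few sentences and less analysis work than a selection procedure for each outcome. It costs a few degrees of freedom, out of 728 − 16 = 712 after a full four-factor model, and the freedom to add covariates later.

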Inclusion Criteria: Parents of children with medical complexity (N=1043, n=35 cognitive testing, n=1008 factorial experiment) who are at least 18 years of age and comfortable reading in English or Spanish. Children with medical complexity is defined as a child (age 0-18 years) with a complex chronic condition defined by ICD-9 or ICD-10 code developed by Feudtner, et al. 2014.

Exclusion Criteria: Exclusion criteria: Parents of children with neuromuscular scoliosis who have not undergone surgery for neuromuscular scoliosis (NMS) to avoid unduly influencing their decision-making process for NMS treatment. NMS will be defined as qualifying ICD-9 or ICD-10 codes for neuromuscular scoliosis (e.g. ICD-9 737.43, ICD-10: M41.40-7, M41.4). NMS surgery will be identified by documentation of spinal fusion in the medical history or orthopaedic clinic note in the medical chart.

Design

Non-Experimental and/or Descriptive Research Design

Interviews and Focus Groups

Experimental and/or Interventional Research Design

Randomized Trial

Study Procedures

Recruitment/ Participant Identification Process:

1,043 children (children of parent participants) will only be involved to identify their parents as eligible but will not complete any further study procedures. No PHI will be included in the research record.

Recruitment will occur at the University of Utah/Primary Children's Hospital (main campus and Lehi campus) as well as a secondary site, Children's Hospital of Los Angeles (CHLA). This section describes the recruitment processes at the main site (UofU/PCH). See below section for a brief description of recruitment processes at CHLA.

1,043 parents (participants) will be recruited using purposeful sampling to achieve a diversity of parent race/ethnicity representative of local demographics. We will also purposefully sample by patients' (children of parents) categories of complex chronic conditions as defined by the Feudtner 2014 classification. 35 parents will be recruited during vignette development for cognitive testing of the vignette (with 15 patients from our secondary site CHLA). The remaining 1,008 parents will be recruited during the factorial experiment (with 237 patients from our secondary site CHLA). See below section for more information on the recruitment process at our secondary site CHLA.

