We will use careful data collection and data management to minimize missing data. If missing data are present in Aim 1 or Aim 3, we will explore patterns of missingness and then impute missing data. We will use the multivariate imputation via chained equations (MICE) approach on both the outcome and predictor variables to create 40 imputed data sets (Graham, et al. 2007)¹⁴⁸, after which coefficients and standard errors are combined using Rubin's rules (Rubin, 1987).¹⁴⁹

Sample size and power calculation for the primary analysis

In a validation study of PrepDM in orthopedic decision making, the scale had mean \pm SD of 3.7 \pm 1.0 after the decision aid intervention. We will randomize n=91 subjects into each of the 2x2x2x2=16 cells of the 4-way factorial design (each factor at 2 levels), for a total N=728 subjects. This is a sufficient sample size to include 4 main effects, 4 two-way interactions, and 3 3-way interactions, without overfitting the data. This provides 80% power, using a two-sided alpha 0.05 comparison, to detect an adjusted mean difference of 3.7 \pm 1.0 vs. 3.4 \pm 1.0 (0.3 standardized mean difference) between the two levels of the factor. That is smaller than a 0.5-point difference on the scale of each item and has been achieved in previous studies of decision aids in orthopedics.

References

2. O'Connor AM. Validation of a Decisional Conflict Scale. *Medical Decision Making*. 1995/02/01 1995;15(1):25-30. doi:10.1177/0272989X9501500105
4. Institute NC. Health Information National Trends Survey (HINTS). Accessed August 5, 2020, 2020. <https://hints.cancer.gov/default.aspx>

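### The SAP's sample-size sentence is arithmetically impossible (91 × 16 = 1,456, not 728), and its total, per-cell number and power conflict with the protocol

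*SAP*

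**What the plan says.** Four places give a size for the factorial experiment.

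- **SAP, Sample size and power calculation for the primary analysis:** "We will randomize n=91 subjects into each of the 2x2x2x2=16 cells of the 4-way factorial design (each factor at 2 levels), for a total N=728". The section then says "This provides 80% power, using a two-sided alpha 0.05 comparison", for a 0.3 SD difference between the two levels of a factor.
- **Protocol, Statistical Methods, Sample size:** "We will randomize n=46 subjects into each of the 2x2x2x2=16 cells of the 3-way factorial design (each factor at 2 levels), for a total N=736". It claims 95% power for the same difference at the same two-sided alpha of 0.05.
- **Protocol, Recruitment/Participant Identification Process:** "The remaining 1,008 parents will be recruited during the factorial experiment". The inclusion criteria give the same split, 35 for cognitive testing and 1,008 for the experiment, 1,043 in all.
- **Protocol, Procedures, Randomization:** "we will randomize each participant to receive one of eight possible versions of the clinical vignette or clinical vignette and narrative information sheet". A hedged sentence about possibly having up to eight versions follows, and then n=63 with the words "parents will be randomized to each version".

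On the number of cells, the SAP's General Considerations gives 16 scenarios from four two-level factors, and its Study Design section describes 16 arms one by one. The protocol's data-analysis paragraph also gives 16 conditions.

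**The concern.** A sample-size sentence should let a reader multiply the number per cell by the number of cells and obtain the total. The SAP's does not, and the error is a factor of two. The protocol's figures do not show which part is wrong, because its own sections differ on the total, on the number per cell and, in the randomisation text, on the number of versions.

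At stake is the reference against which enrolment and precision are judged. With no single target, actual enrolment cannot be compared with a pre-specified number. The per-cell number also governs the interaction estimates, which both documents intend to model and for which sample size matters most. The stated power would normally help to identify the intended total; here it does not.

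**Working it through.** **Inputs.** SAP sample-size section: 91 per cell, 16 cells, total 728, power 80%. Protocol sample-size paragraph: 46 per cell, 16 cells, total 736, power 95%. Protocol recruitment text: 1,008. Protocol randomisation text: 8 versions, 63 each. Effect 0.3 (3.7 against 3.4), SD 1.0, two-sided alpha 0.05, equal cells. Neither sample-size section states a dropout allowance.

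**Step 1: the SAP's own figure.** 91 × 16 = 1,456, not 728. In the other direction, 728 / 16 = 45.5, which is not a whole number. 91 × 8 = 728, so the printed pair fits only an 8-cell design.

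**Step 2: the protocol's figures.** 46 × 16 = 736 multiplies correctly, but four two-level factors make a four-way design, not a three-way one. 63 × 8 = 504, a total that is printed nowhere. 63 × 16 = 1,008, which matches the recruitment text. 35 + 1,008 = 1,043, which matches the overall sample.

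**Step 3: main-effect power at each total.** A main effect compares half the sample with the other half, so its standard error is 2·SD/√N. Power = Φ(0.3·√N/2 − 1.96), and the 95% confidence interval half-width is 1.96 × 2/√N in SD units. For N = 728: 0.3 × 26.98/2 − 1.96 = 2.09, and Φ(2.09) is about 0.982.

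**Step 4: interaction power.** The documents give no interaction effect size. I assume a two-way difference-in-differences of 0.3 SD. Its standard error is 4·SD/√N, so power = Φ(0.3·√N/4 − 1.96).

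| Total N | Status | Main-effect power at 0.3 SD | Main-effect CI half-width (SD) | Two-way interaction power (assumed 0.3 SD) |
|---|---|---|---|---|
| 504 | implied, 63 × 8 | 92.0% | 0.175 | 39% |
| 728 | printed, SAP | 98.2% | 0.145 | 53% |
| 736 | printed, protocol | 98.2% | 0.144 | 53% |
| 1,008 | printed, protocol | 99.7% | 0.123 | 66% |
| 1,456 | implied, 91 × 16 | >99.9% | 0.103 | 82% |

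The noncentral t distribution gives the same main-effect powers to within about 0.1 percentage point.

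**Step 5: totals that the stated powers would need.** Per level, n = 2(1.96 + z)²/0.3². For 80%, z = 0.842 gives 175 per level, so N = 350. For 95%, z = 1.645 gives 289 per level, so N = 578. Two variants do not recover 728 either: at 80% power, one-sided alpha needs 276, and alpha divided by 4 needs 496.

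**The case against.** The strongest reply is that these are leftovers from an earlier design and that the intended design can still be seen. Sixteen cells are well supported: the SAP names every arm, in the past tense, and the protocol's data-analysis paragraph agrees. The figure of 63 multiplied by 16 is exactly the recruitment figure. The totals 728 and 736 differ by only 8, which is what rounding 45.5 up to 46 per cell would give. The SAP's analysis section is also headed as of May 2023, so the figures may date from different stages. All this is plausible, and the case for 16 cells stands. But the documents do not say that any figure is superseded, and a date cannot rescue a product that fails within one sentence.

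The 1,008 might be 736 enlarged for incomplete responses. That would need a loss of 1 − 736/1,008 = 27%. Neither sample-size section mentions an allowance, and the 736 is described as the number to randomise.

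The stated powers might be read as lower bounds, or the 80% as referring to a factor's effect within one level of another factor. With 728 in all, that compares 182 with 182 and has 81.6% power. But the SAP describes the comparison as between the two levels of the factor, and neither reading explains 80% in one document and 95% in the other at almost the same total.

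A reader might also infer three stronger things that the documents do not support.

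- **That the fourth factor could not be estimated from eight versions.** A suitably chosen half-fraction of eight arms estimates four main effects clear of two-way interactions. It could not support the full four-way model with its interactions. Nothing suggests that an eight-arm list was built.
- **That the totals differ almost threefold.** That ratio divides 1,456 by 504, and neither is printed. The printed totals run from 728 to 1,008, a ratio of about 1.4.
- **That nobody can say what recruitment aimed at.** The protocol gives 1,008 consistently in its inclusion criteria and recruitment text. The defect is that neither sample-size section agrees with it.

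**Conclusion.** The point holds as an error of arithmetic and consistency that must be corrected. The SAP's per-cell number and total cannot both be right for 16 cells, and they are out by a factor of two. The protocol adds two further printed figures, 736 and 1,008, and a randomisation text with eight versions. The target total, the number per cell and the interaction precision are therefore undefined, and the stated powers of 80% and 95% correspond to none of the totals.

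It would be wrong to conclude that the primary comparison is underpowered. For a main effect of 0.3 SD with SD 1.0, equal cells and no loss of participants, power is about 92% at the smallest implied total and about 98% or more at every printed one. The interaction powers, from 39% to 82%, rest on an assumed effect of 0.3 SD and show only that the choice of total matters there. The documents do not show which of 91, 46, 63, 728, 736 or 1,008 was meant; explanations by carry-over from an eight-cell design are inference.

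**What to change.** In both documents, state one design (16 cells, four two-level factors, four-way), one number per cell, and one total that is their product and agrees with the recruitment figure. Two pairs multiply correctly and use printed totals: 63 × 16 = 1,008, or 46 × 16 = 736 with the recruitment text reconciled to it. The sponsor must confirm which was the target. Then:

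- correct the SAP's 91 and 728 to the confirmed target;
- change eight versions to sixteen in the protocol's randomisation text, and three-way to four-way in its sample-size paragraph;
- replace the 80% and 95% with the power at the confirmed total (about 98.2% at 736, about 99.7% at 1,008) and say which comparison it refers to;
- state any allowance for incomplete responses if one was made;
- report actual enrolment against the confirmed target. Because the SAP already describes randomisation in the past tense, date the correction and label it as such.

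The cost is wording in two documents and a short recalculation. If the target was 736 or 1,008, the correction itself calls for no more participants than the recruitment text already plans. That cannot be promised outright: if 91 in each of 16 cells was really meant, 1,456 exceeds the recruitment figure by 448.
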